8.4.1. Handling of Missing Data for Complete Clearance Endpoint

The efficacy endpoint, proportion of subjects exhibiting complete clearance of all treatable warts, is to be assessed during the study. Assessments are to be done at Treatment Visit 2, Treatment Visit 3, Treatment Visit 4, the EOT visit and follow-up visits at Day 105, Day 126 and Day 147.

Subjects who do not have an assessment of complete clearance of all treatable warts in a particular visit window for any of the scheduled assessments will be considered to have missing data for this endpoint at that visit. The primary method to handle missing data will be to assign all subjects with missing clearance data as not having achieved complete clearance. For additional considerations related to assessments of clearance, see Section 8 (Efficacy Analysis).

8.4.2. Handling of Missing Data for Treatable Wart Count Endpoints

Assessment of number of treatable warts is planned for the baseline visit, each visit where treatment is applied, the EOT visit and three follow-up visits. Endpoints that are based on these assessments include percent reduction from baseline in the number of treatable warts, change from baseline in the number of treatable warts, proportion of subjects exhibiting 50% or greater reduction in the number of treatable warts from baseline and proportion of subjects exhibiting reduction of at least 1 treatable wart from baseline. If the number of treatable warts is not available, the number of treatable warts will be imputed from earlier assessments of wart count using last observation carried forward (LOCF). The LOCF method uses information from the last available assessment of the measurement to include subjects with missing data in analysis.

When applicable, LOCF will be used to impute other post baseline treatment visits when the assessment of number of treatable warts is not available. An exception includes the following:

- If Treatment Visit 2 is missing, LOCF will not be used to impute a result for Treatment Visit 2. No result collected prior to first dose will be carried forward.

Imputation for missing wart area will be carried out using the same methods described above when imputing for missing number of treatable warts.

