All treated subjects (including dropouts) will be evaluated in the intent-to-treat population. Those subjects who do not complete the full treatment due to lack of protocol adherence or who request to be discontinued from the study will be replaced. In the event a subject request to be removed from the study due to study-related adverse experiences or additional

spreading of disease, data will be collected and analyzed as a treatment failure and the subject will be replaced. Further discussion of how treatment failure will be utilized in analysis will be provided in the statistical analysis plan.

If a subject subsequently becomes able to provide informed consent (turns of legal age while on study) or a legally authorized representative is located after enrollment, information about the trial should be provided and procedures from the IRB/ethics committee will be followed. The subject or legally authorized representative can withdraw consent at any time during the study and for any reason without any penalty or changes to care. Data collected to the point that consent is withdrawn are still assessable by the principal investigator. If subjects do not want their data that has already been submitted or collected specimens utilized, they will need to submit a request in writing to the Investigator for removal of their information.

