8.2 Premature Study or Site Termination

If the Sponsor, investigator, medical monitor, study monitor, or appropriate regulatory officials discover conditions arising during the study that indicate that the study should be halted or that the site should be terminated, this action may be taken after appropriate consultation among the Sponsor, investigator, medical monitor, and study monitor. Conditions that may warrant termination of the study include, but are not limited to, the following:

- The discovery of an unexpected, serious, or unacceptable risk to the subjects enrolled in the study
- A decision on the part of the Sponsor to suspend or discontinue testing, evaluation, or development of the product
- A study conducted at a single site in a multicenter study may also warrant termination under the following conditions:
 - Failure of the investigator to enroll subjects into the study at an acceptable rate
 - Failure of the investigator to comply with pertinent regulations of appropriate regulatory authorities
 - Submission of knowingly false information from the site to the sponsor, study monitor, or appropriate regulatory authority
 - Insufficient adherence to protocol requirements

Study termination and follow-up will comply with the conditions set forth in International Council for Harmonisation (ICH) E6, Guideline for Good Clinical Practice. Data from all sites, including those that have been terminated for non-compliance or unsatisfactory enrollment will be evaluated and included in the interpretation of study findings. Subjects from sites that terminate early will be considered for analysis. If a subject does not complete the study, they will still be counted as a failure for the primary endpoint.

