8.1. Efficacy Variables

Primary endpoint:

- Proportion of subjects exhibiting complete clearance of all treatable warts (baseline and new) at the End of Treatment (EOT) Visit (Day 84).

Secondary endpoints:

- Change from baseline in the number of treatable warts (baseline and new) at the EOT visit (Day 84).
- Change from baseline in the percent of treatable warts (baseline and new) at the EOT visit (Day 84).
- Proportion of subjects exhibiting complete clearance of all treatable warts (baseline and new) at Treatment Visit 2, Treatment Visit 3, Treatment Visit 4.

Exploratory endpoints:

- Percent reduction of all treatable warts (baseline and new) from baseline at Treatment Visit 2, Treatment Visit 3, Treatment Visit 4.
- Change from baseline in the number of treatable warts (baseline and new) at Treatment Visit 2, Treatment Visit 3, Treatment Visit 4.
- Proportion of subjects exhibiting $\geq 50\%$ clearance of all treatable warts (baseline and new) at the EOT visit as compared to baseline.
- Proportion of subjects who respond to treatment defined by a $\geq 50\%$ reduction in total wart area at EOT visit compared to baseline.
- Proportion of subjects exhibiting reduction of at least 1 treatable wart from baseline at Treatment Visit 2, Treatment Visit 3, Treatment Visit 4 and at the EOT Visit.
- Proportion of subjects exhibiting complete clearance of all treatable warts (baseline and new) at follow-up visits on Day 105, Day 126 and Day 147.
- Percent reduction of all treatable warts (baseline and new) from baseline at follow-up visits on Day 105, Day 126 and Day 147.
- Change from baseline in the number of all treatable warts (baseline and new) from baseline at follow-up visits on Day 105, Day 126 and Day 147.

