8.4. Handling of Dropouts or Missing Data

All subjects who receive treatment will be evaluated in the ITT population. In the event a subject requests to be removed from the study due to study related adverse events or additional spreading of disease, data will be collected and analyzed as a treatment failure and not replaced.

Unless described otherwise in subsequent sections, analyses will be carried out with the data available using no imputation for missing data. A description of how missing data as well as warts that combine will be handled for select endpoints is included below.

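### SAP 8.4.2 carries observations forward into three exploratory responder endpoints without excepting withdrawals that SAP 8.4 calls treatment failures; the replacement wording also conflicts

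*SAP*

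**What the plan says.** Protocol 4.4 says that subjects who ask to leave because of study-related adverse experiences or disease spread are analysed as treatment failures, and defers the detail: "Further discussion of how treatment failure will be utilized in analysis will be provided in the statistical analysis plan".

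The SAP, which covers Cohort 2 only, answers in one sentence of section 8.4. For these subjects, "data will be collected and analyzed as a treatment failure and not replaced". No endpoint is named.

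SAP 8.4.1 treats missing clearance as not cleared. SAP 8.4.2 takes a different route for counts: "If the number of treatable warts is not available, the number of treatable warts will be imputed from earlier assessments of wart count using" LOCF. It lists the endpoints concerned, including the two binary ones defined in SAP 8.1: at least 50% "clearance of all treatable warts (baseline and new) at the EOT visit as compared to baseline", and "reduction of at least 1 treatable wart from baseline at Treatment Visit 2, Treatment Visit 3, Treatment Visit 4 and at the EOT Visit". Area follows: "Imputation for missing wart area will be carried out using the same methods described above". The one exception concerns a missing Treatment Visit 2: "No result collected prior to first dose will be carried forward". SAP 9.3 and 9.4, which define the responder tables, do not mention treatment failures.

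On replacement, Protocol 4.4 first says dropouts are not replaced. It then says that non-adherent subjects, those who ask to stop, and adverse-event or spread withdrawals are replaced. SAP 8.4 says adverse-event or spread withdrawals are not. The Protocol Synopsis expects 35 Cohort 2 subjects evaluable at Day 84, while Protocol 9.2.6 and SAP section 4 enrol about 35.

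**The concern.** Two rules in the same SAP can give opposite results for one person. A subject who improved, asked to leave because of a study-related adverse event and was not seen again is a treatment failure under 8.4. Under 8.4.2 the improved count or area is carried to the End of Treatment (EOT) visit, and the subject is a responder. Nothing says which rule prevails, so two programmers could report different responder rates from the same data.

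The reverse gap also exists. Protocol 4.3.1 and 8.1 ask sites to obtain final assessments from subjects who leave early. If such a subject returns and shows a 50% reduction, the SAP does not say whether the observed value or the failure status counts, and LOCF plays no part in that case.

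At stake are three exploratory, descriptive proportions. The replacement conflict is a separate matter: it decides whether the number enrolled can deliver the number the Synopsis expects to evaluate.

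**Working it through.** The plan has no figure to reproduce, because SAP section 4 disclaims a formal sample size. The check applies the written rules to example subjects and sizes the result. Subject-level values and responder counts below are assumed.

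**1. Counts.** Inputs: percent-change formula (SAP 9.2), categories (SAP 9.3). A subject has 4 warts at baseline and 2 at Treatment Visit 3, then asks to leave for a study-related adverse event and has no later assessment.
- SAP 8.4: treatment failure.
- SAP 8.4.1: EOT clearance missing, so not cleared. This agrees with 8.4.
- SAP 8.4.2: the count of 2 is carried forward. It was taken after the first dose, so the exception does not apply. (2 − 4)/4 × 100 = −50%, a responder at the 50% threshold and also on the one-wart endpoint.

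**2. Area.** Input: circle formula with π = 3.14 (SAP 9.4).
- One wart shrinking from 6 mm to 4 mm: (4/6)² − 1 = −55.6%, a responder.
- A spread withdrawal can also qualify. One 8 mm wart (3.14 × 4² = 50.24 mm²) becomes one 4 mm wart (12.56) plus two new 2 mm warts (2 × 3.14 = 6.28), total 18.84 mm². (18.84 − 50.24)/50.24 = −62.5%. The count rises from 1 to 3, so this subject is an area responder but not a count responder.

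**3. Size per subject.** Taking 35 in the ITT population (SAP section 4: about 35), each failure scored as a responder adds 1/35 = 2.9 points. For example, 17/35 = 48.6% becomes 18/35 = 51.4%. Three such subjects would move 15/35 = 42.9% to 18/35 = 51.4%. The exact 95% interval for 15/35 alone is 26.3% to 60.6%.

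**4. Denominator, on one reading.** A failure with no post-baseline count has nothing to carry forward. SAP section 5 leaves missing values out of percentages unless stated otherwise. If that applies, losing one non-responder changes x/35 to x/34:

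| Responders x | x/35 | x/34 | Rise (points) |
|---|---|---|---|
| 9 | 25.7% | 26.5% | 0.8 |
| 17 | 48.6% | 50.0% | 1.4 |
| 26 | 74.3% | 76.5% | 2.2 |

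**5. Does a sensitivity analysis expose it?** SAP 9.2 repeats change and percent change in counts without imputation, follow-up visits included. It does not extend this to the responder categories in 9.3 or to area in 9.4.

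**6. Replacement.** If no one is replaced, any dropout before Day 84 leaves fewer evaluable than enrolled. No dropout rate is given for this trial. As an illustration, the earlier VP-102 studies in Protocol 2.2.2 had non-completion of 1/33, (1 + 4)/30 with both bridging cohorts pooled, and 4/16 in the worse bridging cohort. Then 35 × 32/33 = 33.9, 35 × 25/30 = 29.2 and 35 × 12/16 = 26.3: about 34, 29 or 26 completing.

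**The case against.** The strongest reply is that either natural reading of SAP 8.4 removes the conflict. On one, the failure sentence is a specific rule for a named group; someone already classed as a failure on a yes/no endpoint has an outcome and needs no imputation. On the other, failure means failure to clear. Protocol 8.2 uses the word that way for non-completers: "If a subject does not complete the study, they will still be counted as a failure for the primary endpoint". SAP 8.4.1 would then already carry it out. Both readings are reasonable, but they give different responder rates, and the SAP states neither, although the protocol left the matter to it. The clause in 8.4 that allows later sections to differ qualifies the default of no imputation, not the failure sentence, so it does not settle precedence.

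Three further objections stand:
- A reader might infer that a failure with no post-baseline count certainly leaves the denominator. Section 5 yields where something else is stated, and 8.4 may be that statement, so this is only one reading.
- A reader might conclude that every missing responder visit should count as non-response. The conflict concerns only the 8.4 withdrawals. LOCF for other missed visits is prespecified, and replacing it exchanges one imputation choice for another.
- The 26 to 34 completers come from molluscum studies, not from common-wart subjects aged 12 and over. They are an illustration, not a forecast.

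Spread withdrawals are also less likely to look like count responders, because new warts are counted. Adverse-event withdrawals are the likelier route.

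**Conclusion.** The point holds and is minor. Read literally, SAP 8.4.2 permits a subject whom 8.4 calls a treatment failure to be scored a responder on the count and area endpoints, by up to 2.9 points per subject with 35 in the denominator. That assumes the subject improved before leaving and has no later assessment. The number of such withdrawals is not stated, and the effort to obtain Day 84 data would reduce it.

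A reader might infer that the trial's main result is at risk. The documents do not support that: LOCF does not reach the primary endpoint or clearance by visit, since 8.4.1 sets missing clearance to not cleared. The study is single-arm with no formal comparisons, and the affected responder endpoints are exploratory. Nor do the documents say that failures will be scored as responders, only that nothing prevents it.

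The replacement statements contradict each other. Without replacement, 35 evaluable cannot be relied on from about 35 enrolled. No power figure depends on this.

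**What to change.** In SAP 8.4, state that subjects who withdraw at their own request for study-related adverse events or disease spread are non-responders, and stay in the ITT denominator, for the three responder endpoints (at least 50% count reduction, at least one wart fewer, at least 50% area reduction) at visits after withdrawal. State that this applies whether the value is missing or was collected at a post-withdrawal assessment, and that it takes precedence over LOCF in 8.4.2.

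Keep LOCF for other missing visits and leave the continuous endpoints as planned. Extend the no-imputation sensitivity analysis in SAP 9.2 to the responder tables in 9.3 and the area tables in 9.4.

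Separately, reconcile the replacement statements in Protocol 4.4 and SAP 8.4, by cohort. If Cohort 2 withdrawals are not replaced, change the Synopsis statement of 35 evaluable in Cohort 2 to about 35 enrolled, with fewer evaluable at Day 84.

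The cost is a few sentences in the SAP, a short protocol clarification and some extra tables. No new data are needed. Exploratory responder rates may come out slightly lower.

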2.2.3. Exploratory Objectives

Exploratory objective is:

- to evaluate the efficacy of VP-102 by assessing the proportion of subjects exhibiting complete clearance of all treatable warts (baseline and new) at follow-up visits on Days 105, 126 and 147.
- to assess endpoints other than clearance that may be indicative of treatment efficacy.

3. Study Design

This is a Phase 2, open label, multi-center study [Study number VP-102-105; referred to as COVE-1 (Cantharidin and Occlusion in Verruca Epithelium)] that will be conducted in the United States to determine the safety, efficacy and tolerability of VP-102 treatment in subjects with common warts.

This study has two Cohorts. The second Cohort (Cohort 2) utilizes a treatment interval of 21 days between treatments. Paring of lesions is allowed in Cohort 2 only.

Approximately 35 subjects (12 years and older) will be enrolled in Cohort 2. Up to 4 sites will participate in the study.

All subjects will receive the Study drug VP-102 (0.7% w/v cantharidin topical film-forming solution). Duration of warts prior to Treatment Visit 1 must be at least 4 weeks.

Study drug (VP-102) will be supplied in single-use applicators, with one applicator having sufficient volume to treat 1-6 common warts. No more than 1 applicator will be permitted per subject per treatment. VP-102 will be applied and left on the warts, under occlusive tape, for 24 hours before the subject/guardian removes the occlusive tape and washes the warts with soap and warm water. Occlusive tape and Study drug may be removed prior to the 24-hour time point in the event significant blistering, significant pain or treatment-emergent adverse events (TEAEs) are experienced.

Treatment will be applied up to four times during a 75-day treatment period for Cohort 2. The treatment interval in Cohort 2 is 21 days.

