The study will enroll subjects with common warts for the main efficacy purpose of obtaining information on clearance rates of the warts in response to VP-102 therapy. Subjects will continue to be enrolled into Cohort 2 of the study until approximately 35 subjects are enrolled. Due to the exploratory nature of the study, no formal sample size estimates will be carried out for powering purposes.

5. Statistical Methods

The statistical analyses described in this document are specific to Cohort 2 of this study and will be reported using summary tables, figures and listings (TFLs). Numbering for TFLs will be based on the recommended numbering convention provided by the International Conference on Harmonization. Continuous variables will be summarized with means, standard deviations, medians, minimums and maximums. Categorical

variables will be summarized by counts and percent of subjects in corresponding categories. Where appropriate, 95% confidence intervals may be included. Missing values are not considered for percent calculations, unless stated otherwise. In those cases, footnotes will specify the percent basis.

Individual subject data obtained via the electronic data capture (EDC) system and from external vendors will be presented in listings.

The analyses described in this plan are considered *a priori*, in that they have been defined prior to database lock. Any analysis added after the database lock will be considered *post hoc* and exploratory. *Post hoc* analyses will be labeled as such on the output and identified in the CSR. All analyses and tabulations will be performed using SAS® version 9.3 or higher. Tables and listings will be presented in .rtf or .pdf format. Upon completion, all SAS programs will be validated by an independent programmer. The validation process will be used to confirm that statistically valid methods have been implemented and that all data manipulations and calculations are accurate. Checks will be made to ensure accuracy, consistency with this plan, consistency within tables and consistency between tables and corresponding data listings.

6. Analysis Populations

Intent to Treat (ITT) Population:

The Intent-to-Treat population (ITT) will include all subjects enrolled in the study.

Per Protocol Population:

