7.3. Demographic and Baseline Characteristics

Demographics variables will include: age, sex, ethnicity and race. For summary purposes, age will be derived by comparing date of birth to date of informed consent.

Baseline characteristics will include: relevant medical history, wart history (including prior treatment), Fitzpatrick Skin Type, height, weight and body mass index (BMI). BMI will be calculated by weight (kg) / height (m²). Wart history variables that will be summarized include time since clinical diagnosis (as compared to informed consent), age at clinical diagnosis and any previous treatments for warts. Time since clinical diagnosis will be derived by comparing the date of informed consent to date of clinical diagnosis. Time since clinical diagnosis will be expressed in months using the following conversion: (12 * days) / 365.25. In the event the date of clinical diagnosis is not complete (“partial date”), the date will be imputed with the earliest date possible. As an example, if only the month and year are known for date of clinical diagnosis, the first day of the month will be used for imputation purposes.

Age at clinical diagnosis will be derived by comparing date of clinical diagnosis to date of birth. Incidence of the following prior wart treatment categories will be tabulated: Cantharidin, Anti-Virals, Retinoids, Salicylic Acid, Curettage, Freezing, Other. Relevant medical history will not be summarized in a table but will be displayed in a listing.

Continuous variables will be summarized using descriptive statistics. Categorical variables will be summarized using counts and percentages. Demographics, baseline characteristics, wart history and prior wart treatment will be summarized for all 3 analysis populations (ITT, Safety, Per Protocol).

8. Efficacy Analysis

The ITT and Per Protocol population will be used for efficacy analysis. Analyses based on the ITT population will be considered the primary analyses. Results will be summarized using descriptive statistics and counts/percentages. For select endpoints, 95% confidence intervals may be generated as well.

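### ITT wart-reduction response rates leave out subjects with no post-baseline measurement, whom the complete clearance rate counts as failures

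*SAP*

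**What the plan says.** The relevant rules are spread over several sections of the SAP.

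- **Population.** Section 6: "The Intent-to-Treat population (ITT) will include all subjects enrolled in the study". Section 8: "Analyses based on the ITT population will be considered the primary analyses".
- **Complete clearance.** Under 8.4.1 the main method is to "assign all subjects with missing clearance data as not having achieved complete clearance".
- **Wart count endpoints.** Under 8.4.2 a missing count is filled by LOCF, with one limit: "No result collected prior to first dose will be carried forward". Wart area follows the same method.
- **Defaults.** Unless a later section differs, 8.4 says that "analyses will be carried out with the data available using no imputation for missing data". Section 5 adds: "Missing values are not considered for percent calculations, unless stated otherwise". It then promises a footnote giving the basis where a table departs from that default.
- **Failure clause.** 8.4 also says that a subject who asks to leave because of study-related adverse events or spread of the disease is analysed as a treatment failure.
- **Sensitivity analysis.** 9.2 repeats the change and percent change summaries with observed counts only. It does not cover the response rates in 9.3 and 9.4.

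**The concern.** Take a subject who has the first application and is then lost with no further wart measurement. In the clearance table this subject is a failure and stays in the denominator. In the tables for ≥50% count reduction, reduction of at least one wart and ≥50% area reduction, the subject is absent. One ITT table set then has two denominators.

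The comparison matters because a cleared subject has a 100% reduction, so ≥50% reduction contains complete clearance. A reader will set the two rates side by side and take the gap as partial response. Part of that gap could come from the denominator alone.

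The study makes no formal comparisons, and the protocol synopsis says its clearance rates should support assumptions for later placebo-controlled trials. The percentages are the main product, so their basis should be fixed in advance.

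**Working it through.** **Inputs**

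- N = 35. SAP Section 3: "Approximately 35 subjects (12 years and older) will be enrolled in Cohort 2". This is a target without a calculation (SAP Section 4), so the plan has no figure of its own to reproduce.
- k = number of ITT subjects with no post-baseline wart measurement. The documents do not give it. Assumed range: 0 to 4.
- x = number of responders. Not given. Assumed: 20, with 10 and 24 as alternatives.

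**Step 1: which subjects are affected.** 8.4.2 bars the baseline value, so a subject with nothing later has no count or area at any visit. Nothing in 8.4.2, 9.3 or 9.4 overrides the Section 5 default, and 9.3 has only two categories, with none for missing. Such subjects can occur. In Cohort 2, protocol Table 2 schedules no wart measurement at Unscheduled visits, so a subject seen only at such visits before leaving would have none.

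**Step 2: size for the yes/no endpoints.** The SAP rule gives x/(N − k). The clearance rule gives x/N. The difference is xk / [N(N − k)], which is never negative. With x = 20, x/N = 20/35 = 57.1%.

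| k | SAP rule | Difference (points) |
|---|---|---|
| 0 | 20/35 = 57.1% | 0 |
| 1 | 20/34 = 58.8% | 1.7 |
| 2 | 20/33 = 60.6% | 3.5 |
| 3 | 20/32 = 62.5% | 5.4 |
| 4 | 20/31 = 64.5% | 7.4 |

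At k = 3 the difference is 2.7 points for 10 responders (10/32 against 10/35) and 6.4 points for 24 (24/32 against 24/35).

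**Step 3: effect on the comparison with clearance.** Suppose 18 of the 20 responders also cleared, so clearance is 18/35 = 51.4%. With k = 3 the gap between ≥50% response and clearance is shown as 62.5 − 51.4 = 11.1 points. On a common denominator it is 57.1 − 51.4 = 5.7.

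**Step 4: the failure clause.** If f of three affected subjects are kept as failures under 8.4, the rate is 20/(32 + f): 62.5%, 60.6%, 58.8% and 57.1% for f = 0, 1, 2 and 3. Full application closes the gap. The clause reaches only subjects who ask to leave for the two named reasons. Loss to follow-up, noncompliance, intercurrent illness and consent withdrawn for other reasons fall outside it. The SAP also never says what failure means for a count, a percent change or an area, although protocol 4.4 leaves that explanation to the SAP.

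**Step 5: change and percent change.** If the k subjects are set to zero change, a mean m in the others becomes m(N − k)/N. For m = −60% (assumed), this is −60 × 34/35 = −58.3% at k = 1 and −60 × 32/35 = −54.9% at k = 3.

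**Step 6: planned checks.** The observed-only run in 9.2 omits the same subjects, so it cannot show the effect.

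**The case against.** The strongest reply has four parts.

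1. *The failure clause already handles the leavers who matter.* It sits in the parent section, is not limited to clearance, and for a yes/no endpoint reads most naturally as non-response. This stands in part. A reader might infer that every early leaver drops out of the response rates. The text does not support that. What remains is the subjects lost for other reasons, and the lack of any statement on how the clause applies.

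2. *The rates are not shown to be wrong.* This stands. A reader might infer bias against the true response rate. If the three missing subjects would have responded like the other 32, the expected rate is (20 + 3 × 0.625)/35 = 62.5%. The SAP figure is then right and 57.1% is too low. Refusing to treat a pre-dose count as an on-treatment result is also a defensible choice.

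3. *Few subjects, if any, will be affected.* One post-baseline measurement inside the Day 11 to 157 windows supplies a value. Cohort 2 must attend all visits, and sites are to seek Day 84 assessments after withdrawal. Non-completion in the earlier VP-102 molluscum studies was 1 of 33 and 5 of 30 (protocol 2.2.2), and having no post-baseline data is narrower than non-completion. This stands as a limit on size, and zero is possible.

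4. *The tables will show much of this.* Section 5 promises footnotes on departures from the default, and protocol 9.2.1 requires the non-missing n for continuous data. A careful reader could find the exclusion for change and percent change. Showing it does not put the response rates and clearance on one basis.

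**Conclusion.** The point holds in a limited form. In the ITT analysis, subjects with no post-baseline wart measurement who fall outside the failure clause leave the three yes/no reduction rates but stay in the clearance rate as failures. Those rates are therefore equal to or higher than under the SAP's own clearance rule. For 35 enrolled and an assumed 20 responders, the difference runs from 0 (none affected) to 7.4 points (four affected). The number affected and the number of responders are both assumptions.

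The three yes/no endpoints are exploratory; change and percent change at EOT are secondary. The primary endpoint is unaffected. So are the Per Protocol EOT results, because that population requires an EOT clearance assessment.

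A separate difference exists. A subject with some post-baseline data but no EOT value is carried forward for counts and scored as a failure for clearance. Aligning the denominators does not remove it. The point is worth correcting because the change is cheap and specific.

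**What to change.** - **SAP 8.4.2, 9.3 and 9.4:** for the three yes/no endpoints, count every ITT subject with no post-baseline value as a non-responder, with the full ITT denominator. State that this includes subjects under the 8.4 failure clause.
- **SAP 8.4.2 and 9.2:** for change and percent change, keep the rule against carrying baseline forward. Add one sensitivity run with these subjects set to no change.
- **Table footnote:** state that subjects with some post-baseline data but no EOT value are carried forward for counts and scored as failures for clearance.

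The cost is a few SAP sentences, one extra run and a footnote. No new data are needed. Reported response rates may become slightly less favourable, and they will be conservative if the missing subjects would have responded like the others.
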